### 9.7.1 Main analysis

We will compare the outcome of interest both in unmatched and propensity score matched patient sets as described below. The primary analysis will be on propensity score matched patient sets and we will compare the post-approval >80 year old patients with the pre-approval retrospective >80 year olds regarding baseline demographics, clinical and radiological parameters, as well as treatment logistics, safety outcomes, functional outcome and death. Secondary analysis will be on unmatched patient sets, i.e. all patients fulfilling the inclusions-exclusions criteria will be included in this analysis. A sensitivity analysis restricted to European and non-European patients might be considered if minimum sample size required for analysis is met in the matched patient set.

Patient sets analysed includes “unmatched” and “matched”. “Unmatched” patients set composed of IV thrombolysis treated patients >80 years from both pre-approval and post-approval phase those who fulfil the inclusions-exclusions criteria. Matched patient set constitute propensity score matched pair (1:1 greedy nearest neighbour matching using calipers equal to 0.2\*SD of the logit of the propensity score).

The incidence rate and corresponding 95% CI of patients with primary and secondary outcome events will be calculated within the following cohorts:

- a) Patients >80 years after approval
- b) Patients >80 years before approval

The incidence rate for the outcome of interest using as-treated approach will be calculated on the unmatched (all eligible patients) and the matched patient sets.

In the primary analysis, post-approval >80 year old patients will be matched to pre-approval >80 year old patients using a structured, iterative propensity score model with the primary objective to maximize the balance in the distribution of possible confounders between these two groups [9].

In the propensity score-matching algorithm, all baseline characteristics will be included. The corresponding propensity score of the post-approval >80 years group will be calculated for

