## 9.8        **QUALITY CONTROL**

European Stroke Centres (approx. 60) continuously registering patients into SITS-ISTR having

- a typical experience from acute stroke treatment
- high quality (at least 90% complete data entered at acute phase and 70% data entered at 3m follow up) in both prospective and retrospective groups
- a willingness to participate in SITS-IVT>80 years registry

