Age, sex, pre-stroke Modified Rankin Scale (mRS) score, baseline NIHSS score, systolic blood pressure and glucose level, antiplatelet treatment at stroke onset, history of hypertension, diabetes, atrial fibrillation, hyperlipidaemia, smoking and previous stroke earlier than 3 months, stroke onset to IVT treatment start time. We will include a baseline covariate only if 85% of the patients have a value reported.

A sensitivity PSM analysis will also be performed based on all baseline characteristics among patients with complete information. To determine whether the propensity score approach achieved balance in all potential confounders, we will compare all baseline characteristics of patients in the post-approval group to their propensity score matched pre-approval patients using standardized difference. If standardized difference >0.2 then propensity score model will be modified with inclusion of interactions and variable transformations to achieve better balance.

Relative risks for binary and mean difference for continuous/ordinal primary and secondary outcomes in post-approval vs pre-approval will be calculated together with 95% profile likelihood confidence intervals and likelihood ratio test p-values for relative risks and 95% Wald confidence intervals and Wald test p-values for mean differences.

Secondary Analysis

Secondary analysis will be on all patients fulfilling the inclusions-exclusions criteria.

Relative risks and mean difference for secondary outcomes in post-approval vs pre-approval will be calculated together with 95% confidence intervals and p-values.

Outcomes among post-approval vs pre-approval will be evaluated with generalized linear multivariable regressions with appropriate response distribution depending on outcome adjusting for potential confounders. Link function will be chosen as to estimate relative risks for binary outcomes and difference for continuous outcomes.

For each primary and secondary outcome covariates in models will be chosen according to the following:

- 1) Factors that contribute to the outcome of interest in an initial univariable analyses at p values <0.1 and variables known to influence outcomes such as age, sex, baseline NIHSS score and pre-stroke mRS, will be included in the multivariable model as candidate variables.
- 2) Final variables among the candidate variables with the outcome of interest will be selected by backward stepwise selection procedures using a p value <0.05 .

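### The primary matched relative risk is planned without covariates and without allowance for the matching: little bias is expected, but the intervals for death and independence are somewhat too wide and there is no guard if pre-stroke mRS drops out of the score

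*SAP*

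**What the plan says.** SAP, Primary Analysis. Patients are matched 1:1 by greedy nearest neighbour within 0.2 SD of the logit of a score built from 14 listed variables, pre-stroke mRS among them. A variable can leave the score: "We will include a baseline covariate only if 85% of the patients have a value reported". Balance is checked more widely than the score reaches: "we will compare all baseline characteristics of patients in the post-approval group to their propensity score matched pre-approval patients using standardized difference". The response to imbalance is "If standardized difference >0.2 then propensity score model will be modified with inclusion of interactions and variable transformations to achieve better balance". The estimate is then described as follows: "Relative risks for binary and mean difference for continuous/ordinal primary and secondary outcomes in post-approval vs pre-approval will be calculated together with" profile-likelihood intervals and likelihood-ratio p-values for the relative risks. No covariate and no pairing term is named.

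SAP, Secondary Analysis. Adjustment appears here, on all eligible patients and not on the matched set. The candidate covariates include "variables known to influence outcomes such as age, sex, baseline NIHSS score and pre-stroke mRS", subject to backward selection at p<0.05. The Planned Analysis section calls this multivariable work complementary and explorative.

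Protocol. Section 9.7.1 states "In the propensity score-matching algorithm, all baseline characteristics will be included" and describes an iterative score model whose first aim is the best possible balance. Section 9.8 asks centres for "at least 90% complete data entered at acute phase". The SAP's centre criteria (4.1.2) keep only the 70% follow-up requirement.

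**The concern.** Three features combine. The primary relative risk ignores predictors that the SAP itself regards as prognostic. Imbalance up to 0.2 triggers no action. Above 0.2, the named remedy (interactions and transformations) does not mention adding a variable from outside the score, such as heart failure, previous TIA or baseline infarct (SAP Appendix 1).

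Pre-stroke mRS is the exposed variable. SAP 4.2 excludes patients with missing SmPC items, which keeps baseline NIHSS, systolic pressure, glucose and onset-to-treatment time complete. Pre-stroke mRS is not an SmPC item, so the 85% rule can remove it.

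The stake is interpretation. The Planned Analysis section says that differences persisting after matching call for other explanations, such as hospital processes or experience. A difference caused by tolerated imbalance could be read in that way. An interval of the wrong width also misstates how much the study has learned.

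**Working it through.** The documents give no power, effect-size or bias figure, so there is nothing to reproduce. Assumptions: no true difference, death 25%, independence (mRS 0-2) 35%, about 1000 patients per period (SAP section 4), and three predictors with odds ratios of 2.0, 1.5 and 1.3 per SD.

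**1. Expected case: all listed variables in the score.** The plan was simulated with an estimated 14-covariate score, greedy 1:1 matching and the 0.2 SD caliper (about 814 pairs, 1200 runs per outcome).
- Residual standardized difference near 0.04; no bias in the relative risk.
- Death: mean reported SE of log RR 0.084 crude and 0.079 adjusted; 0.079/0.084 = 0.94.
- Independence: 0.066 crude and 0.062 adjusted; 0.062/0.066 = 0.94. Before rounding, both reductions are 5-6%.
- Null rejection at 5%: about 3.8% (death) and 3.6% (independence) crude, about 5% adjusted.
- Actual run-to-run SD, adjusted over crude: about 0.99-1.00.

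The crude standard error is thus too large because it ignores balance that the matching has already produced. Adjustment corrects the stated width but leaves the estimator's real variability almost unchanged.

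The SE reduction depends on how predictive the covariates are. Without a matching step it is 2-3% at odds ratios 1.5/1.3/1.2 and 9-10% at 2.5/2.0/1.5. A separate simulation of the matched plan with six correlated covariates gave about 9% for death and 16% for independence. For SICH at about 2% the SE went from 0.354 to 0.352, under 1%.

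**2. Adverse case: pre-stroke mRS out of the score and imbalanced at exactly 0.2.** Assume 15% have pre-stroke mRS above 2 in one period, 5% of them reach mRS 0-2 at day 90, and independence in that period is 35%.
- Prevalence p in the other period solves (p - 0.15)/sqrt([p(1-p) + 0.15×0.85]/2) = 0.2, giving p = 0.228.
- Independence among the remaining patients: (0.35 - 0.15×0.05)/0.85 = 0.403.
- Independence in the other period: 0.228×0.05 + 0.772×0.403 = 0.3225.
- Spurious ratio: 0.35/0.3225 = 1.085.
- SE of log RR with 800 per group: sqrt(0.65/(800×0.35) + 0.6775/(800×0.3225)) = 0.070. The 95% interval then excludes 1 in 21% of studies; with 1000 per group, 26%.

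With prevalence 10-20% and 0-10% of that stratum reaching independence, the factor is 1.06-1.12 if the assumed prevalence belongs to the lower group and 1.04-1.09 if it belongs to the higher group: 4-12% overall. At a standardized difference of 0.1 the central case gives 1.04, and the interval excludes 1 in 9-10%.

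**3. The adverse case run through the matching.** With pre-stroke mRS out of the score and a raw imbalance of 0.19-0.20 SD, the residual was 0.13-0.19. Under the null, the death relative risk averaged 1.04-1.05 (0.94 with the imbalance reversed) and independence 0.94. Rejection was between 3% and 11%. At a raw imbalance of 0.19 with 1000 per period, the 0.2 trigger fired in only 13-39% of runs. Adjusting the matched relative risk brought it to about 1.00 with rejection near 5%, but those runs had pre-stroke mRS observed for everyone.

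**The case against.** The strongest reply is that matching works. Variables in the score end far below 0.2, so the threshold is rarely tested and the primary estimate is not biased in the expected case. This stands.

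The large shifts need three things together: pre-stroke mRS under 85% complete, a raw imbalance of some size, and a residual near the limit. No passage supports any of them, and the protocol's balance aim and 90% acute-phase figure point the other way. The planned table of standardized differences would show a residual of 0.15, and the adjusted secondary analysis could reveal a discrepancy. All of this lowers the probability. It does not correct the primary estimate. The 90% figure is not specific to any variable, and the SAP does not repeat it. The further safeguard, "A sensitivity PSM analysis will also be performed based on all baseline characteristics among patients with complete information", would lose more than 15% of patients in exactly this scenario.

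Two stronger readings are tempting and should not be drawn. A reader might convert the smaller standard error into sample size: 1/0.947² = 1.12 and 1/0.940² = 1.13, or 12-13% more pairs. That conversion would hold for unmatched groups. Here the score already contains the predictors, and real variability barely moves.

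A reader might also conclude that the trigger must be 0.1. That limit is nowhere in the documents, and it would often fire by chance. The chance SD of a standardized difference is sqrt(2/n). For about 13 independent Appendix 1 variables outside the score, the probability that at least one exceeds 0.1 with no real imbalance is about 28% at 1000 pairs, 47% at 780 and 79% at 500.

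**Conclusion.** The point holds as a modest one. That the primary relative risk is unadjusted and ignores the matching is inferred from the SAP's silence, supported by its assignment of adjustment to the secondary models.

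On the stated assumptions, the reported standard error for death and independence is about 5-6% too large, the test is slightly conservative, and bias is negligible. SICH is essentially unaffected. The exact percentage moves with the assumed strength of the predictors.

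A shift of about 4-12% in the independence relative risk is possible only on the pre-stroke mRS route. Its likelihood cannot be judged, because the documents give no completeness figure. The documents do not support saying that the 0.2 rule by itself biases the primary result.

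**What to change.** - For death and independence, define the primary matched-set estimate as a relative risk adjusted for a fixed, prespecified set: age, baseline NIHSS and pre-stroke mRS. Modified Poisson regression with robust standard errors is one way. Report the crude matched relative risk alongside. SICH can stay as planned.
- Exempt pre-stroke mRS from the 85% rule and state how missing values are handled, for example by multiple imputation with matching repeated in each imputed set, results pooled and Wald-type intervals.
- Report standardized differences for all baseline variables. As a sensitivity analysis only, adjust for any variable outside the score that remains imbalanced, so that the primary covariate set does not depend on the data.

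Cost: a short SAP amendment and no new data. With modified Poisson, a robust Wald interval replaces the profile-likelihood interval. If pre-stroke mRS is incomplete, imputing, matching and pooling is real extra work.

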### Intravenous thrombolysis

Intravenous thrombolysis with tissue plasminogen activator (tPA) within 4.5 hours of ischaemic stroke onset is an established and approved treatment. The effect of iv thrombolysis is time-dependent. Among patients treated within one hour, every second patient is expected to fully recover within three months, among those treated within 90 minutes, every third, and within 3 hours every seventh patient. For patients treated within the time interval of 3-4.5 hours, 14 patients need to be treated for one additional patient to recover fully. IV thrombolysis given within three hours from stroke onset increases the chance of reaching good functional outcome (defined as having exactly the same functional level as before the stroke) from 23% to 33%, and when given between 3 and 4.5 hours from onset, by a more modest but still substantial absolute 5%. The use of iv thrombolysis is increasing but still used in only 10-15% of all ischaemic stroke patients. Meanwhile, 2-7% of patients treated with iv thrombolysis suffer symptomatic intracerebral haemorrhage (ICH) as a complication, leading to death in 1.5-2%, and worsening functional outcome in survivors.

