each subject and a nearest neighbour matching algorithm will then be used to match patients in the post-approval >80 years group to patients in the pre-approval >80 years group within 0.2\*SD of the logit of the propensity score. To determine whether the propensity score approach achieved balance in all potential confounders, we will compare all baseline characteristics of patients in the post-approval >80 years group to their propensity score matched pre-approval >80 year old patients using standardized difference.

We will also compare baseline characteristics between the unmatched and propensity matched subgroups to detect potential imbalances between the two populations. Differences of outcome between post-approval >80 years and pre-approval >80 years will be evaluated with univariable and multivariable binary logistic regression models adjusting for potential confounders. In these models the factors that contribute to the outcome of interest in the initial univariable analyses at p values <0.1, will be included in the multivariable model as candidate variables. The final variables that will be independently associated in the multivariable logistic regression analyses with the outcome of interest will be selected by backward stepwise selection procedures using a p value <0.05.

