What is the aim of the analyses: To show, if there are differences between pre- and post-approval populations in the safety, outcomes and in the baseline parameters?

Can differences in the outcomes be explained by differences in the baseline parameters?

Primary analyses: Propensity score matching should diminish differences in the outcomes if patients have balanced baseline parameters. If differences persist or an improvement or worsening of outcomes in the post approval phase occurs, other explanations are needed (as processes in the hospital (shorter or longer of door to needle time or increase of experience). This might need further exploration

Secondary analyses:

To confirm the results of the PS matching by adjusting the model parameter “post-approval vs pre-approval patient” for the most important imbalanced confounders for the outcomes of interest.

Descriptive statistics (absolute and relative frequencies for categorical variables, means, standard deviations, medians, inter quartile ranges, minimum and maximum for continuous/ordinal variables) for baseline, demographic characteristics and outcomes for all included patients will be provided separately for pre-approval and post-approval patients. In addition, 95% Wald confidence intervals will be provided for the continuous outcomes and Wilson score interval with continuity correction for binary outcomes. To compare difference among demographic and clinical baseline characteristics between pre-approval and post-approval, standardized differences will be used. Propensity score matching will be the primary statistical approach, multivariable modeling will be used for secondary complementary explorative analysis.

Primary Analysis

The primary analysis will be on propensity score matched patient datasets and we will compare the post-approval with the pre-approval patients regarding baseline demographics, clinical and radiological parameters, as well as treatment logistics, safety outcomes, functional outcome, and death.

Matched patient set constitute propensity score matched pair (1:1 greedy nearest neighbor matching using calipers equal to $0.2 \times \text{SD}$ of the logit of the propensity score)¹. The primary propensity score will be based on the variables listed below. These variables were selected based on established clinical significance and relevant SmPC criteria available in the SITS database.

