Collinearity will be considered for selection of final list of covariates. Final model will be presented for each outcome with estimates of all final factors together with 95% confidence limits and p-values

Sensitivity Analysis

A sensitivity analysis restricted to European and non-European patients might be considered if minimum sample size required for analysis is met in the matched patient set.

References

1. Austin, Peter C. "Optimal caliper widths for propensity-score matching when estimating differences in means and differences in proportions in observational studies." *Pharmaceutical statistics* 10.2 (2011): 150-161.

6 Appendixes

6.1 Appendix 1

SITS Variables names particularly important for this study

Patient/ file code
Country name
Hospital/ Centre code
Gender
Age At Stroke Onset
Participation In Other Trials
Treatment at baseline
Aspirin
Dipyridamole
Clopidogrel
Other Antiplatelet
Anticoagulants- Yes/ No/ Unknown
If yes, specify Anticoagulants- Not specified/ Warfarin/ Dabigatran/ Apixaban/ Rivaroxaban/ Edoxaban/ Other
Heparin/ Heparinoids for Stroke Prevention
Heparin/ Heparinoids for Prophylaxis Deep Venous Thrombosis
Anti-diabetic, oral
Insulin
Antihypertensive, IV
Antihypertensive, oral
Statin
Other treatment

NSAIDS
Risk factors at baseline
Hypertension
Diabetes
Hyperlipidaemia
Smoking
Previous Stroke
Previous TIA
Atrial fibrillation' (AF)
Congestive Heart Failure
Modified Rankin Scale (mRS) Before Stroke
NIHSS score
Systolic Blood Pressure
Diastolic Blood Pressure
Plasma glucose
Cholesterol
Current Infarct CT/MR
Time logistics
Date Time of stroke onset
Date Time Hospital Arrival
Date Time Of imaging
Date Time Of intravenous thrombolysis
Type of Acute Intervention
Intravenous thrombolysis
Intraarterial thrombolysis
• Dose Of Actilyse
24h follow up
NIHSS
Systolic Blood Pressure
Diastolic Blood Pressure
Current Infarct CT/MR
Local Haemorrhage CT/MR
Remote Haemorrhage CT/MR
Cerebral Oedema CT/MR
At discharge/ 7d
Aspirin
mRS Score
NIHSS
Systolic Blood Pressure
Diastolic Blood Pressure
Dipyridamole
Clopidogrel
Other Antiplatelet
Anticoagulants Oral

Anti Diabetic Oral
Antihypertensive Oral
Statin
Other
Type Of Stroke
Type Of Stroke Ischemic
Type Of Stroke Haemorrhagic
Date Time Of Death
Cause Of Death
At 3-months
Modified Rankin Scale score
If mRS=6=Dead, date/time of death
Cause of death

6.2 Appendix 2

SmPC for Actilyse

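### The secondary regression is meant to adjust for imbalanced confounders, but its selection rule can delete age, sex, NIHSS and pre-stroke mRS; this matters mainly for SICH at a low event rate

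*SAP*

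**What the plan says.** SAP, Planned Analysis, gives the secondary regression a specific job: to confirm the propensity score matching by adjusting the period parameter "for the most important imbalanced confounders for the outcomes of interest". It also sets its rank: "multivariable modeling will be used for secondary complementary explorative analysis".

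SAP, Secondary Analysis, then builds each model in two steps.

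- Step 1 admits factors with univariable p<0.1 against the outcome. In addition, "variables known to influence outcomes such as age, sex, baseline NIHSS score and pre-stroke mRS, will be included in the multivariable model as candidate variables".
- Step 2: "Final variables among the candidate variables with the outcome of interest will be selected by backward stepwise selection procedures", with p<0.05 as the threshold.

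The only other input to selection is one further sentence: "Collinearity will be considered for selection of final list of covariates". Imbalance is measured elsewhere: "between pre-approval and post-approval, standardized differences will be used". It leads to action only in the Primary Analysis, where a standardized difference above 0.2 prompts a change to the propensity score model.

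Protocol 9.7.1 has the same two thresholds (final variables "will be selected by backward stepwise selection procedures using a p value <0.05") and does not name the four variables at all.

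**The concern.** The stated purpose and the rule do not match, in two respects.

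1. The SAP recognises four variables as prognostic and exempts them from the univariable screen, but then exposes them to deletion in step 2. No sentence keeps them. Nor does step 2 say that the period term itself stays, although the purpose implies it.
2. Both steps judge a covariate only by its p-value against the outcome. A variable that differs clearly between the periods but misses p<0.05 is dropped, and its imbalance stays in the estimate labelled as adjusted.

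SICH is a primary safety outcome and is likely to have the fewest events. If its adjusted model may omit NIHSS or age, agreement or disagreement with the matched estimate becomes hard to interpret. The covariate sets will also differ between outcomes partly by chance.

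**Working it through.** The plan states no power, effect size or event count, so there is no figure of its own to reproduce.

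**Inputs from the documents**
- About 1000 patients per period; data exchange may stop short of this once at least 500 European MRP patients are included (SAP section 4).
- SICH rate: "2-7% of patients treated with iv thrombolysis suffer symptomatic intracerebral haemorrhage (ICH) as a complication" (Protocol section 7). This is a general figure for thrombolysis, not specific to patients over 80 or to the SITS-MOST definition.
- Thresholds: p<0.1 to enter, p<0.05 to stay.

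**Expected SICH events** = N × rate. For N=2000: 2000 × 0.02 = 40 and 2000 × 0.07 = 140. For N=1000: 20 and 70.

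**Chance that a real confounder survives step 2.** For a continuous covariate, SE(log RR per SD) = √((1−p)/(Np)). With an assumed RR of 1.3 per SD, log RR = 0.262.
- N=2000, 2%: SE = √(0.98/40) = 0.157; retention 39%.
- N=2000, 7%: SE = √(0.93/140) = 0.082; retention 90%.
- N=1000: retention 22% at 2% and 62% at 7%.
- For an outcome at 33%, retention is about 100% at either size.

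**Bias from one dropped confounder** = exp(d × log RR per SD). With d = 0.2 and RR 1.3: exp(0.2 × 0.262) = 1.054, about 5%.

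**Simulation of the rule as written.** 1000 patients per period, 1500 runs (800 at a 25% outcome), no true period effect, modified Poisson model with robust SE, period term kept. Assumed odds ratios per SD: NIHSS 1.5, age 1.3, pre-stroke mRS 1.2, sex 1.1. Ten further covariates have no effect and are balanced. Unless marked mixed, the four are shifted between periods in the same direction. Excess = exp(mean paired log RR difference, rule minus all covariates forced) − 1.

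| Outcome rate, shift | Rule | Four kept | All forced | Excess |
|---|---|---|---|---|
| 2%, 0.2 SD | 1.065 | 1.000 | 1.001 | 6.4% |
| 2%, 0.1 SD | 1.038 | 1.006 | 1.006 | 3% |
| 4%, 0.2 SD | 1.043 | 1.005 | 1.004 | 4% |
| 7%, 0.2 SD | 1.023 | 1.000 | 0.999 | 2.4% |
| 25%, 0.2 SD | 1.002 | 0.997 | 0.997 | 0.5% |
| 2%, 0.2 SD, mixed directions | 0.994 | 1.007 | 1.007 | −1.3% |

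Share of runs in which step 2 drops each variable:

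| Rate | NIHSS | Age | Pre-stroke mRS | Sex |
|---|---|---|---|---|
| 2% | 0.28 | 0.59 | 0.78 | 0.90 |
| 4% | 0.05 | 0.39 | 0.64 | 0.86 |
| 7% | 0.00 | 0.17 | 0.46 | 0.83 |
| 25% | 0.00 | 0.00 | 0.07 | 0.52 |

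**Against sampling error.** At 2% and 0.2 SD the excess is 0.062 log units and the SD of the estimate is about 0.33. The unadjusted SE of the period log RR is √(2 × 0.98/(1000 × 0.02)) = 0.313, so its 95% CI spans a factor of exp(1.96 × 0.313) = 1.85 each way. Coverage was 0.942 under the rule and 0.953 with the four kept; another run gave 0.944 and 0.947. No loss of coverage is shown.

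**Sensitivity to the assumptions**
- Separate code, same effects, 2%: 1.057 vs 0.996 and 1.060 vs 0.999.
- Four equal confounders at RR 1.2 or 1.3 per SD, 2%: 1.074 or 1.087 under the rule; 0.995 or 1.006 with all four in.
- 500 per period, 7%: 1.041 vs 0.999 in one run and 1.054 vs 1.008 in another. At the minimum size the gap is not confined to the 2% end.
- Stress case with four further same-direction confounders (odds ratios 1.4, 1.3, 1.2, 1.1), 0.2 SD: at 2%, 1.165 under the rule, 1.096 with the four kept, 1.025 with all forced; at 7%, 1.051, 1.029 and 1.005. With the eight in mixed directions at 2%: 0.996, 0.997 and 0.999.

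**The case against.** The strongest reply is that nothing practical changes. At 2% and 0.2 SD, keeping the four moves the root mean squared error only from 0.338 to 0.331; at 0.1 SD it is 0.332 either way. The analysis is explorative. The primary propensity score lists all four variables, and a sensitivity matching on all baseline characteristics gives a second check free of p-value selection. Final models and baseline standardized differences are reported, so a reader can see when an imbalanced variable was dropped. All of this stands and limits the size of the point.

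Same-direction shifts of 0.2 SD in every confounder are also a stress test. The design restricts both periods alike: NIHSS 4 to 25, blood pressure limits, no thrombectomy, centres active in both periods, and, where the country cap applies, patients closest to approval. That is fair, and the stress case with eight confounders should not be read as a forecast.

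The stated aim can be read as giving weight to importance for the outcome, which partly supports selection on the outcome. Even so, it also says imbalanced, and the rule makes no use of that.

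The change is not always free. If 15% of patients lacked pre-stroke mRS and the rule refitted on everyone once that variable dropped out, the root mean squared error was 0.351 under the rule and 0.367 with the four kept. If the complete-case set is fixed at the start of step 2, this loss disappears. The plan does not say which applies.

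**Conclusion.** The concern holds. As written, step 2 can remove the four variables the SAP itself calls prognostic, and no selection step uses balance, so the rule does not deliver the stated aim. The textual gap is certain; its size is illustrative. For SICH near 2% with 1000 per period and a consistent 0.2 SD imbalance, the adjusted period RR is about 6% too high. This falls to about 2% at a SICH rate of 7%, and to nearly nothing for common outcomes or imbalances in mixed directions. These sizes rest on assumed prognostic effects, assumed imbalances and independent covariates.

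The bias is below sampling error and does not touch the matched primary analysis. It weakens the secondary regression as a check on the SICH result. The change is worth considering because it is cheap, not because a conclusion is likely to reverse.

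**What to change.** In step 2 of SAP, Secondary Analysis, state that the period term, age, sex, baseline NIHSS and pre-stroke mRS stay in every model whatever their p-value, and that backward selection applies only to the remaining candidates. Put the same sentence in Protocol 9.7.1 so that the two documents agree.

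**Optional.** Also keep any propensity score covariate whose unmatched standardized difference exceeds a pre-specified limit, as far as the number of SICH events allows. With a limit of 0.1, the RR of 1.096 in the stress case falls to 1.025. However, eight covariates plus period leave 40/9 = 4.4 events per term at 2%. Forcing the full propensity score list, or adjusting SICH for the logit of the propensity score, is for the sponsor to weigh.

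**Cost.** Wording only, with complete data: at 2% and 0.2 SD the SD of the period log RR was 0.337 under the rule and 0.333 with the four kept (mean SE 0.322 and 0.326). Age defines eligibility, and missing SmPC data such as NIHSS already exclude the patient, so only sex and pre-stroke mRS could be missing. If 15% lacked pre-stroke mRS (the most the SAP tolerates for a propensity score covariate) and were lost, the SE would widen by 1/√0.85 = 1.085, about 8%. It would help to state which patients the backward selection uses.
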